14.1 Definition of Study Completion

A patient who completes 26 total infusions of study drug and follow-up visits through Extension Day 785 (± 3) or 84 (± 3) days after last dose or if skipped doses are being made up will be recorded as having completed the study.

14.2 Early Discontinuation of Study Drug

A patient may be discontinued from study treatment at any time if the patient, the Investigator, or the Sponsor feels that it is not in the patient's best interest to continue. The following is a list of possible reasons for study treatment discontinuation:

- Patient withdraws consent.
- Adverse event that, in the opinion of the Investigator, results in it being in the best interest of the patient to discontinue study treatment.
- Protocol violation requiring discontinuation of study treatment.
- Participation in any other trial during the duration of this trial.
- Use of a non-permitted concomitant drug, without prior approval from the Medical Monitor.
- Loss of ability to freely provide consent through imprisonment or involuntary incarceration for treatment of either a psychiatric or physical (e.g., infectious disease) illness.

If a patient is withdrawn from treatment due to an adverse event, the patient will be followed and treated by the Investigator until the abnormal parameter or symptom has resolved or stabilized.

All patients who discontinue study drug treatment should be encouraged to continue on study and complete assessments and procedures according to [Table 1](#), if possible.

Reasonable attempts will be made by the Investigator to provide reasons for patient withdrawals. The reason for the patient's withdrawal from the study will be specified in the source documents.

15. Statistical Methods and General Considerations

This section outlines the nature and rationale for the statistical methods to be used for the analysis of the data from the study. A separate Statistical Analysis Plan will describe data handling and statistical techniques in full detail. The Statistical Analysis Plan will contain any modifications to the analysis plan described below.

All patient data will be listed. When appropriate, summary statistics of number of non-missing values, mean, median, standard deviation, minimum, and maximum will be computed for continuous variables and summary statistics of number and percentage will be computed for categorical variables. No formal statistical inferences will be made. No imputation will be used for missing data.

15.1 Sample Size

Approximately 60 patients will be enrolled.

15.2 Data Sets Analyzed

All patients who have received study medication will be included in the Safety population for safety analysis.

15.3 Demographic and Baseline Characteristics

The following demographic and baseline variables will be summarized:

- Demographics
- Extension Day 1 predose vital signs and laboratory tests

15.4 Patient Disposition

The number and percent of patients who complete or discontinue from the study will be summarized. The reasons for study discontinuation will be included in the summary.

15.5 Analysis of Safety Endpoints

Adverse Events: All AE will be coded using the Medical Dictionary for Regulatory Activities (MedDRA) and will be classified by MedDRA system organ class and preferred term. Listings will include all AE collected on study. The summaries of AE will be based on TEAE, defined as an AE reported in the clinical database with a date of onset (or worsening) on or after the start date of the first intravenous infusion of the study medication.

Patient incidence (N and %) of TEAEs will be summarized as follows:

- Overview of TEAE to include
 - Number (%) of patients who report at least 1 TEAE overall, by severity and by relationship
 - Number (%) of patients who report at least 1 serious TEAE
 - Number (%) of patients who report at least 1 TEAE leading to treatment discontinuation
 - Number (%) of patients who report at least 1 TEAE of special interest
- TEAE by preferred term
- TEAE by system organ class and preferred term
- TEAE by maximum severity, system organ class, and preferred term
- Drug-related TEAE by system organ class and preferred term
- TEAE leading to withdrawal by system organ class and preferred term
- Serious TEAE by system organ class and preferred term
- TEAE of special interest by system organ class and preferred term

Clinical Laboratory Assessments: Samples will be obtained for the clinical laboratory tests identified in Section 11.4, and laboratory tests to be summarized include blood chemistry, hematology, urinalysis, and ADA.

Descriptive statistics will be used to summarize laboratory results at baseline, each visit, and the change from baseline for each visit. In addition, shift tables will summarize the laboratory results relative to normal reference ranges at baseline and each post-baseline time point.

Vital Signs: Vital signs will be summarized at baseline, each visit, and change from baseline at each visit.

Physical Examination: New or worsening symptoms in the symptom-directed physical examinations will be included in the by-patient data listings.

Concomitant Medications: All medications will be coded using the most current World Health Organization Drug Dictionary. Concomitant medications will be summarized by Anatomical Therapeutic Chemical Class and preferred term.

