2.3 Overview of Clinical Studies

AK002, administered as an intravenous infusion has been previously tested in healthy volunteers and in patients with indolent systemic mastocytosis (ISM), chronic urticaria (CU), severe allergic conjunctivitis (AC), mast cell gastritis, and eosinophilic gastritis (EG) and/or eosinophilic duodenitis (EoD), which was previously referred to as eosinophilic gastroenteritis (EGE) in previous versions of this protocol.

Multiple doses of 3 mg/kg AK002 have been given to patients with ISM, CU, severe AC, mast cell gastritis, and EG and/or EoD. In these studies, patients reported improvements in disease symptoms with AK002 pharmacodynamic (PD) activity being observed for prolonged periods of time and AK002 pharmacokinetic (PK) parameters demonstrating [REDACTED]
[REDACTED].

To date, over 300 healthy volunteers and patients with ISM, CU, severe AC, EG/EoD, EoE, and mast cell gastritis have been enrolled in clinical studies. In total, 65 EG/EoD patients were enrolled in the double-blind Study AK002-003 for which this protocol is the open-label extension.

In general, AK002 has been well tolerated. The most common treatment-emergent adverse events (TEAE) observed were infusion-related reactions (IRR). Most IRR were mild to moderate, and 2 IRR were classified as serious but resolved within 24 hours. Common symptoms of IRR were headache, nausea, sweating, flushing, and redness. Most IRR that occurred during the infusion could be managed by slowing or temporary interruption of the infusion, with minimal intervention. Transient lymphopenia was observed after infusion of AK002 but was not associated with any clinical consequence, and lymphocytes recovered within 24 hours. A sustained depletion of eosinophils was observed that is consistent with the mechanism of action of AK002. In 6 healthy volunteers who received 2 doses of 0.3 mg/kg, 4 weeks apart, the second dose was better tolerated than the first dose. This was also the case in patients with ISM, CU, severe AC, and EG/EoD, with fewer adverse events (AE) reported during the second and subsequent infusions when compared to the first infusion.

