In the randomized, double-blind, placebo-controlled Phase 2 study of AK002 in 65 patients with EG and/or EoD, patients were randomized to receive monthly doses of placebo, low dose AK002 (0.3, 1, 1, and 1 mg/kg), or high dose AK002 (0.3, 1, 3, and 3 mg/kg) in a 1:1:1 ratio (Dellon, 2020). All primary and secondary endpoints were met in the study. There was a 97% and 92% mean reduction in eosinophils in the stomach/duodenum at the high dose and low dose, respectively, versus 10% increase on placebo ($p<0.0001$).

The reduction of eosinophils was associated with a statistically significant reduction in total symptom score (TSS) on 8 symptom intensity scores (TSS8) of 58% in the high dose group and 49% in the low dose group versus 24% reduction in the placebo group ($p=0.0012$ and $p=0.015$, respectively). Improvement in symptoms was observed within 24 hours of the first dose of study drug. In addition, 70% of high dose treated patients and 68% of low dose treated patients were treatment responders (defined as $>30\%$ improvement in TSS and $>75\%$ reduction from baseline in tissue eosinophils) versus 5% for placebo treated patients ($p<0.0001$).

When patients complete Study AK002-003 or are discontinued from treatment due to high eosinophil counts prior to infusions 2, 3, or 4, they are eligible to enter this open-label extension study, AK002-003X.

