Proton pump inhibitors have little to no benefit in patients with EG or EoD, despite reports of providing partial benefit in some patients with EoE (Katz, 2013). Restricted/elemental diets are not effective long-term treatment as they require strict compliance and, in the case of elemental diets, are expensive and often not reimbursed by insurance. In addition, compliance is very poor and patient quality of life is greatly impacted (Bedell, 2018; Peterson, 2013; Wechsler, 2014).

Corticosteroids, systemic or swallowed, have been shown to provide symptom relief but are not appropriate for long-term treatment due to numerous side effects and associated risks including adrenal insufficiency, bone demineralization, increased chance of infection, osteoporosis, behavioral issues, and weight gain.

By reducing the number of blood and tissue eosinophils and inhibiting the activation of mast cells, AK002 may be useful in the treatment of patients with EG and/or EoD. This premise is supported by the Phase 2 data with AK002 that shows significant improvements in histology and symptoms in these patients.

Given there are no approved therapies for these chronic and debilitating diseases, better treatment options are clearly needed to manage EG and EoD.

3. Rationale for Study and Dose Selection

Based on experience with AK002 in healthy volunteers and in patients with ISM, CU, severe AC, mast cell gastritis, and EG/EoD, the proposed AK002 dose regimen is up to 26 monthly intravenous infusions of AK002.

In the randomized, double-blind, placebo-controlled Phase 2 study of AK002 in 65 patients with EG and/or EoD, 2 dose levels were evaluated: a lower dose regimen (4 monthly doses of AK002 at 0.3, 1, 1, and 1 mg/kg) and a higher dose regimen (4 monthly doses of AK002 at 0.3, 1, 3, and 3 mg/kg). [REDACTED]

[REDACTED]

[REDACTED]

A starting dose of 1 mg/kg AK002 followed by a dose of 3 mg/kg AK002 for the subsequent infusions has been chosen for the Phase 2 extension study with AK002 in patients with EG and/or EoD.

4. Study Objective

The objective of the study is to generate open-label, longer-term safety, tolerability, and efficacy follow-up data in patients with EG and/or EoD who completed Study AK002-003 or were discontinued from treatment due to high eosinophil counts prior to infusions 2, 3, or 4.

The objective of this extension study is also to give patients that received placebo in Study AK002-003 access to AK002.

5. Study Design

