5.1 Study Overview

This is a Phase 2, multicenter, open-label, extension study to evaluate the safety, tolerability, and efficacy of AK002 in patients with EG and/or EoD. Patients who complete Study AK002-003 will have the option to receive AK002 in an open-label manner. A patient will be categorized as having completed Study AK002-003 if 4 infusions of study drug are administered and the patient is followed through Day 113 (± 3 days).

Patients who were discontinued from treatment in Study AK002-003 at the recommendation of the unblinded safety monitor for high eosinophil counts prior to infusions 2, 3, or 4, will have the option to receive AK002 in an open-label manner.

Patients who enroll in Study AK002-003X will receive monthly AK002 infusions for a maximum of 26 intravenous doses. During Extension Study AK002-003X, patients will maintain the same patient number that was assigned in Study AK002-003.

Safety will be assessed by body weight, vital signs, symptom-directed physical examination, complete blood count (CBC) with differential, blood chemistry, urinalysis, and assessment of AE (including adverse events of special interest [AESI] and serious adverse events [SAE]). In addition, blood samples will be obtained for evaluation of anti-drug antibodies (ADA).

This extension study does not include fasting requirements. Patients underwent a standardized baseline evaluation of eating habits, food habits/restrictions, and food avoidance behaviors during Study AK002-003 and will be asked at study visits whether any changes have been made from the baseline diet.

Patients completing Study AK002-003 and wanting to enter the extension study will begin extended dosing on or about Day 113 of Study AK002-003 (following final assessments of Study AK002-003), which will be considered Day 1 of Study AK002-003X. If patients cannot start extended dosing within 45 days of AK002-003 Day 113, current baseline safety assessments must be completed prior to Day 1 of Study AK002-003X. Patients discontinued from treatment in Study AK002-003 due to high eosinophil counts prior to infusions 2, 3, or 4 may begin extended dosing within 6 months of the last dose in Study AK002-003.

Patients discontinued from the AK002-003 study for high eosinophil counts and patients that completed AK002-003 but were not enrolled into AK002-003X within 45 days of Day 113 will require current safety evaluations.

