Patients will receive up to 26 monthly intravenous infusions of AK002 in an open-label manner. The first infusion of AK002 will be 1 mg/kg, and subsequent infusions will be 3 mg/kg.

If a monthly infusion of AK002 is missed the patient will be permitted to make up the missed dose after the 26th month so that all patients have the chance to receive a total of 26 infusions.

An EGD with biopsy will occur on Day 211 (± 3), Day 547 (± 3), and Day 729 (± 3) or 28 (± 3) days after the last dose of study drug, if early termination (ET) or if patient received additional missed doses.

Patients will be followed for 84 (± 3) days after the last dose of study drug. Follow-up visits will occur on Extension Day 736 (± 3), Day 757 (± 3), and Day 785 (± 3) or 35 (± 3), 56 (± 3), and 84 (± 3) days after last dose of study drug, if ET or if patient received additional missed doses.

Total duration of Study AK002-003X will be approximately 28 months if doses are administered monthly and none are missed, or longer, as needed for the patient to receive all 26 doses.

Approximately 60 patients will be enrolled in Study AK002-003X, based on enrollment of Study AK002-003.

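### Section 15.5 plans only pooled patient percentages for TEAEs and infusion-related reactions, so no planned summary separates patients new to AK002 from those already treated

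*Combined protocol and SAP*

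**What the plan says.** Section 15.5 introduces its adverse event tables with "Patient incidence (N and %) of TEAEs will be summarized as follows". The breakdowns are by severity, relationship, system organ class and preferred term, seriousness, withdrawal and special interest. Section 13.3 counts IRRs among the events of special interest. Section 15.2 gives one analysis set: "All patients who have received study medication will be included in the Safety population for safety analysis". Nothing in Section 15 splits these tables by AK002-003 assignment or infusion number, or uses observation time as a denominator.

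The opening of Section 15 adds that "A separate Statistical Analysis Plan will describe data handling and statistical techniques in full detail". It also provides for listing all patient data, and Section 15.5 provides for listing all adverse events.

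Elsewhere the protocol describes a mixed population:

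- Section 4: "The objective of this extension study is also to give patients that received placebo in Study AK002-003 access to AK002".
- Section 5.1: "A patient will be categorized as having completed Study AK002-003 if 4 infusions of study drug are administered", so a completer from an active arm receives a fifth AK002 infusion on Extension Day 1. Patients stopped before infusion 2, 3 or 4 for high eosinophil counts may also enter.
- Section 2.3: the parent study's active regimens were "low dose AK002 (0.3, 1, 1, and 1 mg/kg), or high dose AK002 (0.3, 1, 3, and 3 mg/kg) in a 1:1:1 ratio". Under Section 9.4, everyone starts the extension at 1 mg/kg and then receives 3 mg/kg.
- Section 2.3 names IRRs as the most common TEAE and describes the pattern in earlier patient studies, EG/EoD included: "with fewer adverse events (AE) reported during the second and subsequent infusions when compared to the first infusion".

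Treatment lasts until dose 26 on Day 701, "or longer, as needed for the patient to receive all 26 doses". Adverse event capture ends at Day 785, or 84 days after the last dose for early termination or make-up dosing.

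**The concern.** The protocol itself indicates that its leading adverse event depends on infusion number, and its design brings in patients at different points of that sequence. A single percentage mixes them. A moderate pooled IRR figure could mean moderate risk for everyone, or high risk at first exposure and low risk later.

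AK002-003 does not fill the gap. Its active patients all began at 0.3 mg/kg, whereas former placebo patients begin here at 1 mg/kg. Among AK002-003 patients, only the extension observes a first infusion at that level.

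There is a lesser issue of the same kind. Each patient counts once in the percentage whatever the length of observation, and Section 15.4 summarises completion and discontinuation but not time or infusions received. Since longer-term safety and tolerability is the first stated objective, these tables are a main product of the study.

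**Working it through.** The plan has no calculation to reproduce: enrolment of about 60 follows AK002-003 enrolment and the analysis is descriptive. The dosing schedule is consistent: 1 + 28 × 25 = Day 701, and 701 + 84 = Day 785.

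**1. Share of patients new to AK002.** Section 2.3 gives 65 patients randomised 1:1:1, so 65/3 = 21.7 per arm. If 60 enter and the arms roll over equally (assumption), 60/3 = 20 are new and 40 previously treated.

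**2. Effect of pooling on an IRR percentage.** Let w be the share new to AK002 and D the risk in new patients minus the risk in previously treated patients. Since pooled = w × p_new + (1 − w) × p_prev:

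- p_new − pooled = (1 − w) × D
- pooled − p_prev = w × D

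The documents give no value for D, so a range is shown.

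| Share new | D (points) | Pooled lies below new by | Pooled lies above previously treated by |
|---|---|---|---|
| 20/60 | 0 | 0 | 0 |
| 20/60 | 10 | 6.7 | 3.3 |
| 20/60 | 20 | 13.3 | 6.7 |
| 20/60 | 40 | 26.7 | 13.3 |
| 15/60 | 20 | 15.0 | 5.0 |
| 25/60 | 20 | 11.7 | 8.3 |

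One percentage cannot identify the pattern. Assumed risks of 50% and 20% give (20 × 0.50 + 40 × 0.20)/60 = 30%, and 30% in both groups also gives 30%.

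**3. Effect of unequal observation.** With no missed doses and capture ending 84 days after last dose k, observation is T = 28(k − 1) + 84 days: 84 days (0.23 years) for k = 1, 224 (0.61) for k = 6 and 784 (2.15) for k = 26. The extremes differ 784/84 = 9.3-fold. No dropout rate is given. Suppose a fraction q stops after dose 6 and is observed for only 84 more days, with a constant event rate λ per year:

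- patient-years = 60 × [(1 − q) × 2.146 + q × 0.613]
- crude incidence = (1 − q)(1 − exp(−2.146λ)) + q(1 − exp(−0.613λ))

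| q | Patient-years | Crude %, λ = 0.10 | Crude %, λ = 0.30 |
|---|---|---|---|
| 0% | 128.8 | 19.3 | 47.5 |
| 20% | 110.4 | 16.6 | 41.3 |
| 40% | 92.0 | 14.0 | 35.2 |

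The underlying rate is the same down each column. The fall comes from shorter observation alone, while the denominator stays at 60.

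**4. Precision of a group of 20.** Exact two-sided 95% limits are 27% to 73% for 10 of 20. For 0 of 20 the upper limit is 1 − 0.025^(1/20) = 17%.

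**The case against.** Section 15 presents itself as an outline and leaves detail and modifications to a separate SAP, which could well hold these tables. A reader might infer that the groups will never be separated; the documents do not support that. What stands is that Section 15.5 states a method, and that method pools.

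A reader might also infer that the information is lost. It is not: all adverse events are listed, and the timing and identifiers needed are collected. What is missing is a planned summary.

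Nor do the documents show that the pooled IRR figure will mislead by any particular amount. The table in step 2 is an identity applied to assumed values of D. Prednisone premedication before everyone's first extension infusion may also affect any difference.

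The observation-time argument is the weaker part. Dropout is assumed, a patient stopping after one dose is an extreme, and Section 14.2 asks that patients who stop the drug be encouraged to stay on study, so some would be observed for longer than 84 days after their last dose.

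Finally, a split would not isolate repeat-exposure risk. Exclusion 1 (poor tolerance of earlier AK002) can remove only previously treated patients. That group may include patients with one to three earlier infusions, and low-dose patients who first receive 3 mg/kg here. This objection stands and must accompany any split tables.

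**Conclusion.** The point holds as a cheap improvement to the protocol text. As written, Section 15.5 summarises TEAEs and IRRs only as pooled patient percentages, combining first-ever AK002 infusions with later ones although the protocol reports that adverse events differ between them. With one third of patients new to AK002, the pooled figure misses their risk by two thirds of the between-group difference. That share rests on equal rollover, and the difference itself is unknown and could be nil. The observation-time issue is secondary and depends on assumed early stopping.

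No error rate is at stake, because no formal inference is planned. Laboratory and vital-sign summaries, which are already by visit, are unaffected.

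**What to change.** Amend Section 15.5 and carry the change into the SAP; if the SAP already contains these tables, cite it in Section 15.5 instead.

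1. Present TEAE, serious TEAE and AESI/IRR tables by AK002-003 assignment (placebo; AK002, with low and high dose shown separately where numbers allow), plus total.
2. Report IRR incidence by extension infusion number within those groups, with patients infused as the denominator. Infusion number alone is not enough, because extension infusion 1 is the first AK002 infusion for some patients and a later one for others.
3. Summarise infusions received and patient-years of adverse event observation, stating that the latter includes the 84-day off-drug follow-up. Give exposure-adjusted rates for non-IRR TEAEs as a secondary display, and keep IRRs per infusion.
4. State that the groups are descriptive, that about 20 new patients give wide intervals, that Exclusion 1 selects only the previously treated group, and that this group can include patients with fewer than four earlier infusions.

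The cost is some wording and a few extra tables. No new data are needed: infusion times (Section 9.6), IRR start times (Section 13.4) and unchanged patient numbers linking to AK002-003 (Section 10.1) are already captured. The downside is more output with imprecise, selected subgroup figures.

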11.4.5 Anti-Drug Antibodies

Serum samples for ADA determination will be processed and shipped frozen in accordance with the laboratory manual and laboratory kit instructions. A central laboratory will analyze the sample for ADA using a validated assay method. Blood samples for ADA will also be collected anytime an immunogenicity-related AE occurs.

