13.3 Adverse Events of Special Interest

Adverse events of special interest for this study include:

- Malignancies confirmed by histopathological report. (Mast cells and eosinophils are part of the normal immune response, by decreasing their function, AK002 could theoretically increase the risk of malignancy).
- Parasitic infections confirmed by positive clinical laboratory test. (Eosinophils are especially active in protecting the body from parasitic infections and decreasing their function could theoretically increase the risk of parasitic and opportunistic infections).
- Opportunistic infections (infections known to be more severe or occur more frequently in immunosuppressed populations) as confirmed by positive clinical laboratory test.
- Infusion-related reactions and hypersensitivity reactions, including anaphylaxis.

Beginning from the time of first study drug infusion and ending at Extension Day 785 (± 3) or 84 (± 3) days after the last dose of study drug if the patient is early terminating or if missed doses are being made up, any new AESI must be recorded in the Adverse Event eCRF and designated as an “adverse event of special interest.” If new information related to any previously reported AESI is identified, the appropriate eCRF should be updated.

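### Section 15.5 summarises anti-drug antibodies (ADA) visit by visit as a routine laboratory test; it defines no patient-level ADA incidence, no summary rule for event-triggered samples and no tabulation against infusion or hypersensitivity reactions

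*Combined protocol and SAP*

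**What the plan says.** The synopsis names immunogenicity among the safety endpoints, and Section 6.1 lists ADA. The analysis text is in Section 15.5, under clinical laboratory assessments: "laboratory tests to be summarized include blood chemistry, hematology, urinalysis, and ADA". The next paragraph gives the method: "Descriptive statistics will be used to summarize laboratory results at baseline, each visit, and the change from baseline for each visit", and in addition "shift tables will summarize the laboratory results relative to normal reference ranges at baseline and each post-baseline time point". Neither sentence makes an exception for ADA.

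On sampling, Table 1 note 20 schedules ADA predose at every dosing day up to Extension Day 365, then at Day 533 and Day 736. Section 11.4.5 adds: "Blood samples for ADA will also be collected anytime an immunogenicity-related AE occurs". The by-visit text in Section 12 words the event-triggered sample as optional. Section 13.3 includes among the adverse events of special interest (AESI): "Infusion-related reactions and hypersensitivity reactions, including anaphylaxis".

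The opening of Section 15 sets general rules. Where appropriate, "summary statistics of number and percentage will be computed for categorical variables". Also, "All patient data will be listed", and "A separate Statistical Analysis Plan will describe data handling and statistical techniques in full detail".

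**The concern.** The usual immunogenicity result is a count of patients: how many were ADA-positive at entry, how many became positive later, and whether those patients had more reactions. Section 15.5 specifies patient-level incidence in detail for adverse events but has nothing equivalent for ADA. The outputs it does name fit ADA poorly. A shift table needs a normal range, and the documents give none for ADA. They also do not say whether the assay reports positive/negative, a titre or both.

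Two features of the study add weight. Infusion-related reactions are described as the most common treatment-emergent event, so a reader will look for reactions by ADA status, and no such table is planned. Also, many patients will already have received AK002 in the parent study. For them, ADA at extension entry may already be drug-induced, and comparison with that baseline cannot show it.

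**Working it through.** The plan states no ADA rate and no figure to reproduce. The rates below are assumptions used to show ranges, and complete sampling is assumed.

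**1. Number of samples.** Dosing days are 1 + 28k. Those up to Day 365 have k = 0 to 13, which gives 14 predose samples. Adding Day 533 and Day 736 gives 16 scheduled samples, 15 of them after entry.

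**2. From by-visit rate to ever-positive incidence.** Let p be the rate at each of the 15 visits.
- Same patients positive throughout: incidence = p.
- Visits independent: incidence = 1 − (1 − p)^15.

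| p per visit | same patients | independent visits |
|---|---|---|
| 1% | 1% | 1 − 0.99^15 = 14% |
| 2% | 2% | 1 − 0.98^15 = 26% |

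Independence is not the outer limit. If no patient is positive twice, incidence is 15 × 2% = 30%. The same by-visit table therefore fits very different answers.

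**3. The reverse direction.** Suppose 6 of 60 patients (10%) are ever positive, each at m of the 15 samples, spread evenly over time. An average row holds 6m/15 patients.
- m = 1: 0.4 patients, 0.4/60 = 0.7%.
- m = 3: 1.2 patients, 1.2/60 = 2.0%.
- m = 15: 6 patients, 6/60 = 10%.

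With persistent ADA the table shows the true incidence. With transient ADA it shows much less. The documents do not say which to expect.

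**4. Event-triggered samples.** Of the 26 doses, 12 fall after Day 365, and only Day 533 has a scheduled ADA sample, so 11 have none. The gaps are 533 − 365 = 168 days and 736 − 533 = 203 days. For a late reaction, the event-triggered sample may be the only ADA result nearby. A patient positive only in such a sample adds nothing to any scheduled-visit row.

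**5. Prior exposure.** The parent study randomised 1:1:1 to placebo and two AK002 arms. If extension entry mirrors this, about 60 × 2/3 = 40 patients had AK002 before Extension Day 1 and about 20 had not.

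**6. Precision of a patient-level summary** (exact 95% intervals, N = 60): 0/60 gives 0 to 6.0%; 3/60 gives 1.0 to 13.9%; 6/60 gives 3.8 to 20.5%. For zero events the upper limit is 1 − 0.025^(1/n), so the split by parent-study treatment would give 8.8% for n = 40 and 16.8% for n = 20.

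**The case against.** The best defence is that the protocol section is an outline. Its opening allows n (%) for categorical variables, so a positive/negative ADA result would be shown as a percentage. The laboratory list also contains urinalysis, so it need not be read as imposing one numeric treatment on every test. Section 15.5 speaks of each visit and each post-baseline time point without limiting these to scheduled ones; that limit appears only in Section 15.6, for blood eosinophils. All data are listed, and full detail is left to a separate SAP.

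Much of this stands, and it rules out three stronger readings that a reader might infer.
- *ADA is analysed on the wrong scale.* The documents never state the form of the ADA result, and the general rule permits n (%). The defect is that status and scale are undefined and the stated default is ill-suited.
- *Event-triggered results are lost.* They would be listed. What is missing is a rule for including them in a summary.
- *The study cannot state its immunogenicity result.* With about 60 patients and full listings, ever-positive patients can be counted afterwards. The plan simply does not commit to that count or define it.

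The defence does not supply an incidence definition, a rule for unscheduled samples or a table of reactions by ADA status. A separate SAP could supply all three, but it would have to depart from a method that the protocol states without exception.

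**Conclusion.** The point holds as an ill-suited and incomplete analysis specification for a named safety endpoint, and it should be corrected. The planned outputs do not determine patient-level ADA incidence: an assumed 2% at each of 15 visits fits 2% under full persistence and 26% under independence, and an assumed 6 positives among 60 patients can appear as anything from 0.7% to 10% in an average row. How much would be hidden depends on how persistent ADA is, on which the documents are silent.

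The conclusion rests on the protocol text alone, since the separate SAP could not be checked. The sample size and the descriptive design are unaffected.

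**What to change.** Take ADA out of the change-from-baseline and shift-table sentences in Section 15.5 and add a short ADA paragraph, repeated in the SAP, that does the following.

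- Defines ADA-positive status from the assay output, and evaluable patients as those with an entry result and at least one later result.
- Reports n (%) positive at extension entry, newly positive at any later sample, and boosted (a titre rise in those positive at entry, where titre is available).
- Counts scheduled and unscheduled samples alike.
- Shows these by parent-study treatment (placebo versus AK002), with exact 95% intervals as description only.
- Tabulates infusion-related and hypersensitivity AESI by ADA status.

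A tabulation against blood-eosinophil response should be added only if loss of suppression is first given an analysis definition, which the documents lack.

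Separately, the required wording for event-triggered sampling in Section 11.4.5 and Table 1 note 20 and the optional wording in Section 12 must be reconciled, because the summary depends on which samples exist.

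The cost is one paragraph and one or two tables from data already being collected. Few positives are likely and the split by parent-study treatment widens the intervals, so the table of reactions by ADA status will be descriptive only.
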